7.1.5.2. Expectedness

A serious adverse event that is not included in the Adverse Reaction section of the relevant reference safety information (RSI) by its specificity, severity, outcome, or frequency is considered an unexpected adverse event. The RSI for this study is the IB.

A serious adverse event that is not included in the Listing of Adverse Reactions in the RSI by its specificity, severity, outcome, or frequency is considered an unexpected adverse event.

The sponsor's Global Patient Safety and Pharmacovigilance will determine the expectedness for all serious adverse events.

For the purpose of SUSAR reporting, the version of the IB at the time of occurrence of the SUSAR applies.

7.1.5.3. Reporting a Serious Adverse Event

7.1.5.3.1. Investigator Responsibility

To satisfy regulatory requirements, all serious adverse events that occur during the study, regardless of judged relationship to administration of the IMP, must be reported by the investigator according to the instructions provided on the serious adverse event form. The event must be reported within 24 hours of when the investigator learns about it. Completing the serious adverse event form and reporting the event must not be delayed, even if not all the information is available. The investigator does not need to actively monitor patients for adverse events once this study has ended.

Serious adverse events occurring to a patient after the last administration of IMP should be reported to the sponsor if the investigator becomes aware of them.

The serious adverse event form should be sent to the local safety officer (LSO) or designee (a contract research organization in a country without a sponsor LSO) (contact information is in the Clinical Study Personnel Contact Information section); the LSO will forward the report to the sponsor's Global Patient Safety and Pharmacovigilance.

The following information should be provided to record the event accurately and completely:

- study number
- investigator and investigational center identification
- patient number
- onset date and detailed description of adverse event
- investigator's assessment of the relationship of the adverse event to the IMP (no reasonable possibility, reasonable possibility)

Additional information includes:

- age and sex of patient
- date of first dose of IMP
- date and amount of last administered dose of IMP
- action taken
- outcome, if known
- severity
- explanation of assessment of relatedness
- concomitant medication (including doses, routes of administration, and regimens) and treatment of the event
- pertinent laboratory or other diagnostic test data

- medical history
- results of dechallenge/rechallenge, if known
- for an adverse event resulting in death:
 - cause of death (whether or not the death was related to IMP)
 - autopsy findings (if available)

Each report of a serious adverse event will be reviewed and evaluated by the investigator and the sponsor to assess the nature of the event and the relationship of the event to the IMP, study procedures, and to underlying disease.

Additional information (follow-up) about any serious adverse event unavailable at the initial reporting should be forwarded by the investigator within 24 hours of when it becomes known to the same address as the initial report.

For all countries, the sponsor's Global Patient Safety and Pharmacovigilance will distribute the Council for International Organizations of Medical Sciences (CIOMS) form/Extensible Markup Language (XML) file to the LSO/Syneos Health for submission to the competent authorities, IEC/IRBs, and investigators, according to regulations. The investigator must ensure that the IEC/IRB is also informed of the event, in accordance with national and local regulations.

Note: Although pregnancy is not a serious adverse event, the process for reporting a pregnancy is the same as that for reporting a serious adverse event, but using the pregnancy form (see Section 7.3).

7.1.5.3.2. Sponsor Responsibility

If a serious unexpected adverse event is believed to be related to the IMP or study procedures, the sponsor will take appropriate steps to notify all investigators participating in sponsored clinical studies of TEV-50717 and the appropriate competent authorities (and IEC/IRB, as appropriate).

In addition to notifying the investigators and competent authorities (and IEC/IRB, as appropriate), other actions may be required, including:

- altering existing research by modifying the protocol
- discontinuing or suspending the study
- modifying the existing consent form and informing all study participants of new findings
- modifying listings of expected toxicities to include adverse events newly identified as related to TEV-50717

7.1.6. Protocol-Defined Adverse Events of Special Interest

No protocol-defined adverse events of special interest were identified for this study.

7.1.7. Withdrawal Due to an Adverse Event

Any patient who experiences an adverse event may be withdrawn from the study or from IMP at any time at the discretion of the investigator. If a post-day 1 QTcF value >500 msec or change from baseline (Study TV50717-CNS-30046 or Study TV50717-CNS-30060) or day 1 (Study SD-809-C-17), as appropriate (see Section 9.7.2) >60 msec is found, the investigator should repeat the ECG assessment twice and compare the average of the 2 pre-treatment QTcF values (ie, the parent study baseline and screening values for patients rolling over from Study TV50717-CNS-30046 or Study TV50717-CNS-30060 or the day 1 and screening values from the current study for patient[s] who completed Study SD-809-C-17) to the average of the 3 post-day 1 QTcF values. The IMP must be stopped for any confirmed post-day 1 QTcF value >500 msec or increase from baseline (Study TV50717-CNS-30046 or Study TV50717-CNS 30060) or day 1 (Study SD-809-C-17) >60 msec. If a patient is withdrawn wholly or in part because of an adverse event, both the adverse events page and termination page of the CRF will be completed at that time.

The patient will be monitored at the discretion of the investigator (eg, until the event has resolved or stabilized, until the patient is referred to the care of a health care professional, or until a determination of a cause unrelated to the IMP or study procedure is made). The investigator must inform the clinical project physician (CPP)/clinical leader as soon as possible of any patients who are being considered for withdrawal due to adverse event(s). Additional reports must be provided when requested.

If a patient is withdrawn from the study for multiple reasons that include adverse events, the termination page of the CRF should indicate that the withdrawal was related to an adverse event. An exception to this requirement will be the occurrence of an adverse event that, in the opinion of the investigator, is not severe enough to warrant discontinuation but that requires the use of a prohibited medication, thereby requiring discontinuation of the patient. In such a case, the reason for discontinuation would be need to take a prohibited medication, not the adverse event.

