5.3. Prior and Concomitant Medication or Treatment

Any prior or concomitant therapy, medication, or procedure a patient receives during IMP administration and up to the end of the study period, including follow-up, will be recorded on the CRF. Generic or trade name, indication, and dosage will be recorded. In addition, only for patients who completed Study SD-809-C-17, any prior or concomitant therapy, medication, or procedure a patient has had within 3 months before IMP administration will be recorded on the CRF. The sponsor will encode all therapy and medication according to the World Health Organization drug dictionary.

At each clinic visit after the screening visit, the investigator will ask patients whether they have taken any medications (other than IMP), including over-the-counter medications, vitamins, or herbal or nutritional supplements, since the previous visit. Parents/patients will be instructed during the course of the study to notify the investigator if any new medication is prescribed/administered, including over-the-counter medications. Any prescribed/administered medication should be reviewed with the investigator. Indication, dosage, and start and end dates should be entered on the CRF.

Medications that are allowed, provided that conditions outlined in the table are met, are shown in Appendix A, Table 6.

The medical monitor must be contacted if a patient is receiving (or has to begin or stop receiving during the study) a medication that is associated with QTc prolongation or that is a known strong CYP inhibitor. Addition of a strong CYP inhibitor is prohibited.

Prohibited antipsychotic drugs medications are listed in [Appendix A, Table 7](#), while prohibited medications that are associated with QTc prolongation are listed in [Appendix A, Table 8](#).

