9.7.2. Safety Analysis

All adverse events will be coded using the Medical Dictionary for Regulatory Activities. Each patient will be counted only once in each preferred term or system organ class category for the analyses of safety. Summaries will be presented for all adverse events (overall and by severity), adverse events determined by the investigator to be related to IMP (ie, reasonable possibility [see Section 7.1.4] defined as related or with missing relationship) (overall and by severity), serious adverse events, and adverse events causing withdrawal from the study. Patient listings of serious adverse events and adverse events leading to withdrawal will be presented.

Changes in laboratory and vital signs measurement data will be summarized descriptively.

The use of concomitant medications will be summarized by therapeutic class using descriptive statistics. Concomitant medications will include all medications taken while the patient is treated with IMP.

Observed values in ECG parameters will be summarized, and counts and percentages of abnormal findings will be presented. Changes from parent study baseline (for patients rolling over from Study TV50717-CNS-30046 or Study TV50717-CNS-30060) or from day 1 (for patient[s] rolling over from Study SD-809-C-17) in ECG parameters will be summarized descriptively. In addition, the number and percentage of patients with on-treatment QTcF values >450, >480, or >500 msec and change from baseline (Study TV50717-CNS-30046 or Study TV50717-CNS-30060) or day 1 (Study SD-809-C-17) >30 or >60 msec will be presented.

Observed values in the C-SSRS and observed values and changes from baseline in the CDI-2 (Parent and Self-Report Profiles) will be presented for all patients.

If any patient dies during the study, a listing of deaths will be provided, and all relevant information will be discussed in the patient narrative included in the CSR.

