9.8. Tolerability Variables and Analysis

Tolerability was not specifically defined.

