Stable medications allowed according to inclusion/exclusions criteria	
Antihistamines	Allergies
Melatonin	Insomnia
Allowed strong CYP inhibitors^a	
Bupropion	Antidepressant (aminoketone)
Fluoxetine	Antidepressant (selective serotonin reuptake inhibitor)
Paroxetine	Antidepressant (selective serotonin reuptake inhibitor)

^a The use of these medications will affect the maximum daily dose of IMP, as shown in [Table 2](#).

ADHD=attention-deficit/hyperactivity disorder; CYP=cytochrome P450; IMP=investigational medicinal product; SNRIs=serotonin-norepinephrine reuptake inhibitor.

Note: No dosing changes can be made during the study.

Table 7: Prohibited Antipsychotic Drugs

Typical/first generation antipsychotics	Atypical/second generation antipsychotics
Chlorpromazine	Aripiprazole
Haloperidol	Asenapine maleate
Loxapine	Clozapine
Molindone	Iloperidone
Perphenazine	Lurasidone
Pimozide	Olanzapine
Prochlorperazine	Olanzapine / fluoxetine
Thioridazine	Paliperidone
Thiothixene	Quetiapine
Trifluoperazine	Risperidone
Promethazine-containing compounds	Ziprasidone
Fluphenazine	Tiapride

Table 8: Prohibited QTc Prolonging Drugs

Generic	Class/clinical use	Note
Azithromycin ^a	Antibiotic/bacterial infection	
Chloroquine/Mefloquine	Anti-malarial/malaria infection	
Clarithromycin ^b	Antibiotic/bacterial infection	
Domperidone	Anti-nausea/nausea	Not available in USA

Table 8: Prohibited QTc Prolonging Drugs (Continued)

Generic	Class/clinical use	Note
Droperidol	Sedative; anti-nausea/anesthesia adjunct, nausea	
Erythromycin ⁰	Antibiotic; gastrointestinal (GI) stimulant; GI motility	
Moxifloxacin	Antibiotic/bacterial infection	
Sevoflurane	Anesthetic, general/anesthesia	
Probucole	Antilipemic/hypercholesterolemia	Not available in USA
Sparfloxacin	Antibiotic/bacterial infection	Not available in USA

^a Allowed dose of Azithromycin is up to 500 mg/day

^b Systemic use only. Topical use is allowed.

[figure not shown]
GI=gastrointestinal; USA=United States of America.

Table 9: Other Prohibited Drugs

Generic	Class/clinical use	Note
Cannabidiol oil	Cannabis	Also includes other forms of cannabinoids
Valbenazine	Vesicular monoamine transporter 2 inhibitor	Ingrezza off-label
Quinidine	Class I antiarrhythmic agent	Strong CYP2D6 inhibitor
Terbinafine	Antifungal medication	Weak CYP2D6 inhibitor

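### The coding exception in Section 7.1.7 records some adverse-event-triggered exits as prohibited-medication exits, so the withdrawal-by-reason summary understates them whenever it is used

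*Protocol*

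**What the plan says.** The primary objective (Protocol Section 2.2.1) covers both safety and tolerability. On the second, Section 9.8 says only: "Tolerability was not specifically defined".

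Section 7.1.7 gives a general rule for withdrawals with several reasons, one of them an adverse event: "the termination page of the CRF should indicate that the withdrawal was related to an adverse event". For withdrawals due wholly or partly to an adverse event, "both the adverse events page and termination page of the CRF will be completed at that time". The exception follows. It covers an event that, in the investigator's opinion, "is not severe enough to warrant discontinuation but that requires the use of a prohibited medication, thereby requiring discontinuation of the patient". The instruction is then: "In such a case, the reason for discontinuation would be need to take a prohibited medication, not the adverse event".

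Two planned outputs are affected or may be. Section 9.4.1 summarizes withdrawals by reason. Section 9.7.2 plans a summary and a listing of "adverse events causing withdrawal from the study", alongside all adverse events and related adverse events (each overall and by severity) and serious adverse events.

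The medication limits that can trigger the exception are in Section 5.3 ("Addition of a strong CYP inhibitor is prohibited") and Appendix A. Table 6 places bupropion, fluoxetine and paroxetine among the strong CYP inhibitors, rules out as-needed benzodiazepines and carries the footnote "Note: No dosing changes can be made during the study". Tables 7 to 9 list prohibited antipsychotics, QTc-prolonging drugs (several of them antibiotics) and other drugs.

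**The concern.** In the protocol's own description the adverse event comes first: it creates the need for the drug, and the drug forces the patient out. Without the event there would have been no exit, yet the recorded reason leaves the event out. Whether the exception applies rests on one investigator's opinion of severity, in a study that is open-label for most of its length.

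Most planned safety outputs show how often events occur and how severe they are. The adverse-event withdrawal summary is the only planned adverse-event output that shows events patients could not continue with. Section 5.5 requires the reason for each dose reduction or suspension to be documented, but Section 9.7.2 plans no summary of these. With tolerability undefined, a reader will use the withdrawal figures to judge it, and a coding rule that lowers them bears on the primary objective.

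**Working it through.** No figure in the protocol depends on this rule, so there is nothing to reproduce. The check sets the sections side by side and then shows how the size would scale.

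**Step 1: which outputs use the code.**
- Section 9.4.1, withdrawals by reason: uses the recorded reason, so an exception case appears under prohibited medication. The understatement follows directly.
- Section 9.7.2, adverse events causing withdrawal: the source is not stated. If it is the termination page, the case is lost here too. If it is the adverse-event page, where Section 7.1.2 requires the action taken with the drug and the treatment given, the case can be kept, and this table may then disagree with the disposition table.
- Section 9.7.2, overall adverse-event incidence: unaffected, because Section 7.1.2 records every event whatever its severity or relationship.

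**Step 2: direction.** Against the general rule, the exception moves cases only from the adverse-event reason to another reason. It moves none the other way. The error is therefore zero or downward.

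**Step 3: which events can fall under it.** An event treated with an antipsychotic, a newly added strong CYP inhibitor or a prohibited QTc-prolonging antibiotic could qualify if judged too mild by itself to justify stopping. Depression or suicidality to which the drug may have contributed does not: Section 7.9 (and Section 7.2.2 for the higher ideation levels) ends treatment and participation because of the event itself, and an actual attempt ends participation outright.

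**Step 4: size, by assumption only.** Let p be the true proportion of patients whose discontinuation was triggered by an adverse event and f the share of those coded under the exception. Then:

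reported proportion = p × (1 − f)

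The protocol gives neither p nor f. The assumed ranges are 5% to 15% for p and 0% to 50% for f, with N = 227, the approximate planned enrolment (Section 9.1).

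| True p (patients = p × 227) | f = 0% | f = 10% | f = 25% | f = 50% |
|---|---|---|---|---|
| 5% (11.4) | 5.0% (11.4) | 4.5% (10.2) | 3.75% (8.5) | 2.5% (5.7) |
| 10% (22.7) | 10.0% (22.7) | 9.0% (20.4) | 7.5% (17.0) | 5.0% (11.4) |
| 15% (34.0) | 15.0% (34.0) | 13.5% (30.6) | 11.25% (25.5) | 7.5% (17.0) |

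For example, 10% × (1 − 0.25) = 7.5%, and 227 × 7.5% = 17.0 patients. The relative loss equals f whatever p is.

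**The case against.** The strongest reply is that the rule is an openly stated coding convention with a narrow scope. It covers only events the investigator considers too mild by themselves to justify stopping; anything worse stays under the broad general rule. Leaving is not automatic either: Section 11.1.2 lets the sponsor keep a patient in after a protocol violation, and Section 7.1.8 allows case-by-case deviations because of an adverse event. The derivation of the Section 9.7.2 table can be left to the SAP, and the data needed to recover these cases are collected. Coding by root cause also misclassifies: an unrelated infection needing a prohibited antibiotic would look like a tolerability failure.

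Most of this stands as a limit on the point. The narrow scope and the chance of staying in the study reduce how often the exception applies, but do not change its effect on the disposition table when it does. The point is not that a derivation is missing, because the protocol itself fixes the recorded reason. The infection example is a good reason not to delete the exception or count every such exit as intolerance.

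A reader might infer three stronger things that the protocol does not support:
- **That this is the only output bearing on tolerability.** Section 9.7.2 also plans adverse events by severity, related events and serious events, and Section 9.7.1 adds depression and suicidality scales, vital signs, ECG and laboratory measures.
- **That depression is selectively hidden.** The medication limits make some psychiatric events plausible triggers, but depression or suicidality to which the drug may have contributed is outside the exception. What remains is mainly events judged unrelated or low-grade.
- **That the Section 9.7.2 withdrawal summary is certainly undercounted.** That depends on its source page.

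**Conclusion.** The point holds in limited form and should be acted on. Whenever the exception is used, the Section 9.4.1 summary understates discontinuation triggered by an adverse event. The Section 9.7.2 withdrawal summary does the same if it follows the termination page. The direction is fixed and the size is unknown: nil if no patient falls under the exception, and otherwise a relative loss equal to the share of such exits that are recoded. The percentages above rest wholly on assumed rates and do not predict this trial's results.

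The importance comes from the combination: tolerability is in the primary objective, Section 9.8 does not define it, and this is the only planned adverse-event output tied to stopping treatment. Nothing here shows that the primary objective would be answered wrongly.

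**What to change.** Keep the CRF termination code and the exception as written. In Section 9.7.2, add one derived flag for a prohibited-medication exit triggered by an adverse event, built from the adverse-event record (action taken with the drug and treatment administered, Section 7.1.2) and the concomitant-medication indication (Section 5.3). Tabulate the flagged exits, split by relatedness as recorded under Section 7.1.4, beside the adverse-event withdrawals, and also show the two combined.

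The cost is one derived variable and a few table rows, with no new data collection. The combined discontinuation figure may be slightly less favourable, and it will include some unrelated events, such as infections. The relatedness split makes those visible, so readers can set them aside.

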7.1.8. Protocol Deviations Because of an Adverse Event

If a patient experiences an adverse event or medical emergency, deviations from the protocol may be allowed on a case-by-case basis. To ensure patient safety, after the event has stabilized or treatment has been administered (or both), the investigator or other physician in attendance must contact the physician identified in the Clinical Study Personnel Contact Information section of this protocol as soon as possible to discuss the situation. The investigator, in consultation with the sponsor, will decide whether the patient should continue to participate in the study.

7.2. Psychometric Rating Scales

Site-administered safety scales include the MINI Kid and C-SSRS, and self-administered safety scales include the CDI-2.

7.2.1. Mini International Neuropsychiatric Interview for Children and Adolescents, (version 6.0)

Select MINI Kid modules are administered at screening (only for patients who completed Study SD-809-C-17). Children 13 years of age and under may be interviewed separately or jointly with the caregiver/adult as appropriate or defined by the scale. For children over 13 years

of age, caregiver/adult involvement is strongly encouraged. Questions should be directed to the child, but the caregiver/adult should be encouraged to add relevant information.

The MINI Kid is a short questionnaire to be administered by a trained clinician. The MINI Kid assesses symptoms of psychiatric disorders as outlined in the International Classification of Diseases-10 and the DSM in children 6 to 17 years of age by self-report. For children under 13 years old, the patient may be interviewed separately or jointly with the caregiver/adult as appropriate or defined by the scale, and the caregiver/adult is encouraged to participate when needed. The MINI Kid (version 6.0) is composed of 24 modules overall, and questions are largely yes-or-no questions. The current study will focus on 8 modules: Major Depressive Episode (Module A), (Hypo) Manic Episode (Module D), OCD (Module J), Alcohol Dependence/Abuse (Module L), Substance Dependence/Abuse (Non-alcohol; Module M), ADHD (Module O), Conduct Disorder (Module P), and Psychotic Disorders and Mood Disorders with Psychotic Features (Module R).

A reference sample is provided in [Appendix C](#).

